## **10.2 Audits and Inspections**

Quality assurance personnel may conduct audits to evaluate compliance with the principles of GCP.

If an inspection is requested by a regulatory authority or competent authority (during the trial or after its completion), the Investigator must inform the sponsor immediately.

If an audit or inspection occurs, the Investigator and institution agree to allow the auditor/inspector direct access to all relevant documents and to allocate his/her time and the time of his/her staff to the auditor/inspector to discuss findings and any relevant issues. Participation as an Investigator in this trial implies acceptance of potential inspection by regulatory authorities.

## **11. DATA HANDLING AND RECORD KEEPING**

### **11.1 Electronic Case Report Forms**

Before a trial is initiated the sponsor's representative will review the protocol and eCRF with the Investigators and the study staff.

By signing the Investigator's Agreement, the Investigator agrees to maintain accurate eCRFs and source documentation as part of the case histories for all patients who sign an ICF.

Investigator sites will be provided with access to the eCRF system, which has been fully validated and conforms to 21 Code of Federal Regulations Part 11 requirements. The site staff will be trained on the use of the eCRF including trial specific details before they are able to enter the trial data. Investigational staff will not be given access to the eCRF until they have been trained and assessed as competent to use the system.

Designated investigational staff will enter all requested information (including information entered into the diaries by the patients) required by the protocol into the eCRFs.

To ensure data accuracy, eCRF data for individual patient visits should be completed as soon as possible after the visit. Automated data validation software will check for data discrepancies in the eCRFs and, by generating appropriate error messages, allow modification or verification of the entered data by the investigational staff. The monitor will perform data verification and will document this electronically in the eCRFs. The Investigator or designee must certify that data are complete and accurate within the system by providing electronic approval of the eCRF pages. A reasonable explanation must be given by the Investigator or authorized staff for all missing data. Queries will be sent to the investigational site through the eCRF system. Designated Investigator site staff are required to respond to the queries and make any necessary changes to the data.

Concomitant medications entered into the database will be coded using the WHO Drug Dictionary, which employs the Anatomical Therapeutic Chemical classification system. Medical history or current medical conditions and AEs will be coded using MedDRA terminology.

Corresponding source documentation must support all information recorded in the eCRF. Examples of acceptable source documentation include, but are not limited to, hospital records, clinic and office charts, laboratory notes, and recorded data from automated instruments, memoranda, and pharmacy dispensing records.

Clinical laboratory data required by the protocol will be electronically transferred from the central laboratory to the sponsor or designee. Laboratory results will be provided to the trial site and should be retained with each patient's source data.

## **11.2 Record Retention**

Data on patients collected on eCRFs will be documented in an anonymous fashion and the patient will only be identified by the patient number.

At the end of the trial, the Investigator will receive a copy of the data entered into the eCRF for his or her site. The Investigator will retain the study documents for at least 15 years or as per local laws (whichever is longer). At the end of that period, the Investigator shall notify the sponsor in writing of her/his intent to destroy all such material. The sponsor shall have 30 days to respond to the Investigator's notice; the sponsor may request that the site retains

the materials for a longer duration, at the sponsor's expense. Source documents should be retained according to local laws and institution requirements.

### **11.3 Data Confidentiality**

All data generated from the trial will be regarded as confidential. The monitor(s), the auditor(s), the IRB/IEC, and the regulatory authority(ies) will be granted direct access to the patient's original medical records for verification of trial procedures and/or data, without violating the confidentiality of the patient, to the extent permitted by the applicable laws and regulations and that, by signing a written ICF, the patient or the patient's legally acceptable representative will be authorizing such access. The records identifying the patient will be kept confidential and, to the extent permitted by the applicable laws and/or regulations, will not be made publicly available. If the results of the trial are published, the patient's identity will remain confidential. All data (whether medical or laboratory) generated in the course of the trial will remain the property of the sponsor.

### **11.4 Source Data Access**

Direct access to source data or documents will be permitted during trial-related monitoring, audits, IRB/IEC review and regulatory inspection(s).

### **11.5 Responsibilities Related to Devices**

#### ***11.5.1. Investigator Records and Reports (See [Appendix V - Letter of Approval of Pen Use by the Investigator](#))***

According to the 21 CFR 812.140 and 150 a participating Investigator shall maintain the following accurate, complete, and current records relating to the Investigator's participation in an investigation:

- Record of receipt, use or disposition of a device that relate to:
  - The type and quantity of the device, the dates of its receipt, and the batch number or code mark
  - The names of all persons who received, used, or disposed of each device
  - Why and how many units of the device have been returned to the sponsor, repaired, or otherwise disposed of
- Documents evidencing informed consent and, for any use of a device by the Investigator without informed consent, any written concurrence of a licensed

- physician and a brief description of the circumstances justifying the failure to obtain informed consent. The case history for each patient shall document that informed consent was obtained prior to participation in the trial.
- An Investigator shall prepare and submit the following complete, accurate, and timely reports:
    - An Investigator shall submit to the sponsor and to the reviewing IRB a report of any unanticipated adverse device effect occurring during an investigation as soon as possible, but in no event later than 10 working days after the Investigator first learns of the effect.
    - An Investigator shall report to the sponsor, within 5 working days, a withdrawal of approval by the reviewing IRB of the Investigator's part of an investigation.
    - If an Investigator uses a device without obtaining informed consent, the Investigator shall report such use to the sponsor and the reviewing IRB within 5 working days after the use occurs.
    - An Investigator shall, upon request by a reviewing IRB or FDA, provide accurate, complete, and current information about any aspect of the investigation.

Please see **Appendix V** for instructions regarding the prohibition of promotion and other practices and a format for the letter of approval of pen use by the Investigator (for US sites only).

## **12. PROTOCOL AMENDMENTS, DEVIATIONS AND COMPLIANCE**

Investigators should ascertain that they will apply due diligence to avoid protocol deviations. No waivers to the protocol will be given by the sponsor.

All significant protocol deviations will be recorded and reported in the CSR main body.

These will include variable deviations, for example:

1. Patient not meeting selection criteria but still included in the study
2. Patient continued in the study despite meeting study discontinuation criteria
3. Failure to perform tests or procedures which will impact the interpretation of key endpoints (e.g. safety, efficacy, immunogenicity endpoints) of the study
4. Patient not following treatment regimen mentioned in the protocol

5. Patient taking medications which are prohibited by the protocol, or can have impact on key endpoints of the study
6. GCP not followed.

With respect to inadequate documentation or conduct of SMBG, the following rules will be followed to determine deviations:

- In any given week, if there are missing values for SMBG AND the Investigator documents that the patient is non-compliant, a protocol deviation (for that visit) will be recorded; and listed in the main body of the CSR (as well as in the CSR appendices).
- In any given week, if there are missing SMBG values without accompanying documentation of non-compliance by the Investigator, a protocol deviation (for that visit) will be recorded; but listed only in the CSR appendices, and not in the main body.

Any change to the protocol can only be made in the form of a written amendment to the trial protocol. Depending on the local regulatory requirements, the amendment must be approved by the national authority and/or IEC/IRB before the amendment is implemented.

Only amendments that are required for patient safety may be implemented prior to IEC/IRB approval.

Notwithstanding the need for approval of formal protocol amendments, the Investigator is expected to take any immediate action required for the safety of any patient included in this trial, even if this action represents a violation of the protocol. In such cases, the sponsor should be notified of this action immediately.

## **13. ETHICS**

### **13.1 Institutional Review Board (IRB)/Independent Ethics Committee (IEC)**

Before the start of the study, the protocol, written ICF, and/or other appropriate documents will be submitted to and approved by the IRB/IEC and/or the competent authorities, in accordance with local legal requirements. The study will not commence until written confirmation of their approval has been received by the sponsor or designee. No clinical supplies may be sent to the study sites until the relevant approvals from the IRB/IEC and competent authorities have been obtained.

No patient may undergo any procedure solely for determining eligibility for this trial until the Investigator has received written approval by the IRB/IEC and the regulatory authority.

### **13.2 Ethical Conduct of the Study**

The trial will be conducted in accordance with legal and regulatory requirements, as well as the general principles set forth in the International Ethical Guidelines for Biomedical Research Involving Human Subject (Council for International Organizations of Medical Sciences 2002), Guidelines for GCP (ICH 1996), and the Declaration of Helsinki (World Medical Association 2013). In addition, the trial will be conducted in accordance with the protocol, and applicable local regulatory requirements and laws.

### **13.3 Patient Information and Consent**

All parties will ensure protection of patients' personal information. Patient names will not be included on any forms, reports, publications, or in any other disclosures to the sponsor.

The informed consent document must be in compliance with ICH GCP, local regulatory requirements, and legal requirements. The informed consent document to be used in this trial, and any changes made during the course of the trial, must be prospectively approved by both the IRB/IEC and the sponsor or designee before use.

According to the Declaration of Helsinki, and ICH-GCP, patients must provide their written informed consent prior to enrollment in a clinical trial and before any protocol-specified procedures are performed. Patients must declare their consent by personally signing and dating the informed consent form (ICF).

The patient will also be informed that if she/he wishes to withdraw (see section 6.2) at any time during the trial this will not have any negative consequences to further treatment at the investigational site.

## **14. DEFINITION OF END OF TRIAL**

The end of this trial is defined as the date of the last visit of the last patient participating in the trial (last patient out or last patient last visit). Within 90 days of the end of the clinical trial the sponsor or designee will notify the ECs and regulatory authorities on the completion / termination of the trial as required according to law and regulation.

#### **14.1 End of Trial in a Member State**

End of trial in a Member State of the European Union is defined as the time at which it is deemed that sufficient patients have been recruited and have completed the trial as stated in the regulatory application (i.e., clinical trial application [CTA]) and ethics application in the Member State). Poor recruitment (recruiting less than the anticipated number in the CTA) by a Member State is not a reason for premature termination but is considered a normal conclusion to the trial in that Member State.

#### **14.2 End of Trial in all Other Participating Countries**

End of trial in all other participating countries is defined the date and time of the last patient (patient) last visit.

### **15. SPONSOR DISCONTINUATION CRITERIA**

The sponsor is entitled to terminate the study:

- In case there is evidence that the safety of the trial participants is no longer assured.
- In case the 3001 study interim analysis affects the current favorable patient risk benefit relationship.

Should this be necessary, the sponsor will promptly notify the Investigators; and the Investigators will be informed of the procedures to be followed to assure that adequate consideration is given to the protection of the patient's interest.

Pursuant to law and regulation, the sponsor or Investigator will notify IRB/IECs and regulatory authorities within 15 days of premature termination of the trial, clearly explaining the reasons for premature termination. After notification, the Investigator must contact all participating patients and the hospital pharmacy (if applicable) within 30 days. Trial sites may be asked to have all patients currently participating in the trial to complete all assessments for an early termination visit. As directed by the sponsor, all trial materials must be collected and all eCRFs completed as far as possible.

A specific site may be terminated for unsatisfactory patient enrolment (as long as there are no active recruited patients), insufficient quality, or for improper data recording.

IRB/IECs and regulatory authorities may also terminate the trial prematurely for any reason and at any time following consultation with the sponsor. A decision to prematurely terminate the trial is binding on all Investigators.

## **16. PUBLICATION OF STUDY RESULTS**

Information generated by the trial is the property of the sponsor. Publication or other public presentation of data resulting from this trial requires prior review and written approval of the sponsor.

### **16.1 Communication of Study Results**

This trial will be registered on ClinicalTrials.gov, the EudraCT database and in other trial registries as deemed appropriate. The basic results will be posted at [www.clinicaltrials.gov](http://www.clinicaltrials.gov) in a tabular format within a year from the end of the trial (as defined in the preceding sections) or upon finalization of the CSR, whichever occurs later.

The trial results will be documented in a clinical study report (CSR), in an ICH E3-compliant format. A copy of the final report, duly checked for correctness, completeness, integrity, and accurate representation of data and interpretation of trial outcome, will be issued to Investigators and counter-signed by the global coordinating Investigator; as per the sponsor's SOPs.

### **16.2 Publications by Investigators**

For all publications relating to the trial, institutions will comply with recognized ethical standards concerning publications and authorship, including *Section II - "Ethical Considerations in the Conduct and Reporting of Research"* of the Uniform Requirements for Manuscripts Submitted to Biomedical Journals, <http://www.icmje.org/index.html#authorship>, established by the International Committee of Medical Journal Editors.

Data from individual trial sites must not be published separately. It is agreed that the results of the trial will not be submitted for abstract, presentation, poster exhibition or publication by the Investigator until the sponsor has reviewed and commented on the presentation or manuscript for publication. Abstracts, manuscripts, and presentation materials should be

provided to the sponsor for review and approval at least 30 days prior to the relevant submission deadline.

## 18. APPENDICES

Appendix	Title
I	Questionnaire to Assess Hypoglycemia Unawareness
II	Suggested General Guidance for Insulin Dose Titration
III	4- and/or 8-point Glucose Estimation Time Points
IV	Sample Patient Diary Information
V	Letter of Approval of Pen Use by the Investigator (for US sites only)

### **Appendix I - Questionnaire to Assess Hypoglycemia Unawareness**

*Please circle only one answer for each question.*

1. Have you **lost** the ability to experience symptoms such as sweating, shaking, palpitations, light-headedness, or nervousness when your blood sugar is low?

No / Yes

2. To what extent can you recognize low blood sugar based on symptoms?

Never / Seldom / Sometimes / Often / Always ["Never," "Seldom," or "Sometimes" = Yes]

3. Below which level do you feel that your blood sugar is low?

65 / 60 / 55 / 50 / 45 [55 or below = Yes]

4. During the past year, did you have any low blood sugar episode associated with confusion for which you required assistance from another person?

No / Once / More than once ["More than once" = Yes]

5. During the past year, did you have any low blood sugar episode for which you required intervention from paramedics, an emergency department visit, or an injection of glucagon by another person?

No / Yes

#### ***Diagnosis of Hypoglycemia Unawareness (HUN)***

Patients will be considered to have HUN if 3 of the 5 questions were scored "yes."

References: [8,9].

**Appendix II - Suggested Guidance for Insulin Dose Titration**

Lowest fasting capillary blood glucose (pre-breakfast) value for 3 days	Adjust basal insulin dose (U per dose) (Lantus® or Mylan's insulin glargine)
>270 mg/dL	+ 6 U
181-270 mg/dL	+ 4 U
151-180 mg/dL	+ 2 U
131-150 mg/dL	+ 1 U
71-130 mg/dL (Target level)	Maintain Dose
56-70 mg/dL	-2 U
<56 mg/dL	-4 U

Lowest post-prandial capillary blood glucose value (2 hour post food) for 3 days	Adjust mealtime insulin dose (U per dose) (Insulin lispro)
>270 mg/dL	+ 6 U
201-270 mg/dL	+ 4 U
180- 200 mg/dL	+ 2 U
< 180 mg/dL (Target level)	Maintain Dose

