### **5.7 Administration**

Insulin glargine should be administered as a subcutaneous injection. It should be taken at approximately the same time every day. The preferred site is in the abdomen. The other possible sites of administration are the upper arm and thigh (upper leg). The injection sites should be rotated to reduce risk of lipodystrophy. Refer to the Investigator's Brochure [6] and US prescribing information [7]. Insulin lispro will be administered as per the Investigator's advice and as per the prescribing information [10,11].

The dosage of insulin will be adjusted based on SMBG profile, performed by the patients at home, so that patients attain the following glycemic targets (ADA 2014 criteria) [4]:

- Fasting pre-prandial SMBG between 70 to 130 mg/dL (3.9-7.2 mmol/L)

If the measured SMBG is <70 mg/dL (3.9 mmol/L) or if the patient has symptoms suggestive of hypoglycemia, he/she can call the Investigator or designee, if required. The insulin dose will be altered by the Investigator or designee, if required, based on the values. Any increase in total insulin dose per day of >6 units during any titration step should be performed with caution.

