#### **B. Documented Symptomatic Hypoglycemia**

An event during which typical symptoms of hypoglycemia are accompanied by a measured plasma glucose concentration  $\leq 70$  mg/dL (3.9 mmol/L).

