#### **C. Asymptomatic Hypoglycemia**

An event not accompanied by typical symptoms of hypoglycemia but with a measured plasma glucose concentration  $\leq 70$  mg/dL (3.9 mmol/L).

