#### **7.5.6.3. Management of Hypoglycemia**

The following steps are recommended for managing hypoglycemic episodes:

1. The patient should begin with 15 to 20 grams carbohydrate (e.g., 3-4 teaspoons of table sugar dissolved in water, 1 tablespoon of honey,  $\frac{3}{4}$  cup of juice or regular soft drink, 3-4 glucose tablets).
2. Subsequently, if the glucose level is  $\leq 50$  mg/dL, then the patient will be asked to consume 20 to 30 grams carbohydrate (e.g., 4-6 teaspoons of table sugar dissolved in water, 2 tablespoons of honey,  $\frac{4}{5}$  cup of juice or regular soft drink, 4-5 glucose tablets).
3. Patient will be asked to recheck blood glucose after 15 minutes and to repeat hypoglycemia treatment if the blood glucose does not return to normal after 15

- minutes. If the next meal is more than 1 hour away, patients should follow with additional carbohydrate or a snack.
4. If hypoglycemia persists after the second treatment, patient or companion should be instructed to contact the Investigator.

It is recommended that the patients always carry some sugar lumps, sweets, biscuits, or sugary fruit juice.

**For an event of severe hypoglycemia** the patient can be treated with glucagon (0.5 to 1 mg) given intramuscularly or subcutaneously by a person who has received appropriate training, or glucose given intravenously by a medical professional. Intravenous glucose can also be given if the patient does not respond to glucagon within 10 to 15 minutes. Upon regaining consciousness administration of oral carbohydrate is recommended in order to prevent a relapse.

Full hypoglycemic episode documentation includes time of occurrence, duration, time of recovery, remedial measures undertaken, recording the symptoms and plasma glucose / SMBG levels at the beginning and end of the episode with time and date, and classification in to different subtypes (Refer to section [7.5.6.1](#)).

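### The mealtime insulin table in Appendix II labels post-meal glucose of 70 mg/dL or less as on target, because its lowest row has no floor

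*Protocol*

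**What the plan says.** Appendix II has two tables. The mealtime one is indexed by "Lowest post-prandial capillary blood glucose value (2 hour post food) for 3 days". Its rows are above 270 mg/dL (+6 U), 201-270 (+4 U), 180-200 (+2 U) and finally "< 180 mg/dL (Target level"), for which the dose is maintained. Nothing follows that row.

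The basal table is indexed by the lowest fasting value over 3 days. Its target row is "71-130 mg/dL (Target level"), and two rows lie below it: 56-70 mg/dL (-2 U) and under 56 mg/dL (-4 U).

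Three other parts of the protocol deal with low glucose:

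- Section 7.5.6.1 sets the cut-off at 70 mg/dL or less, both for a documented symptomatic event, where "typical symptoms of hypoglycemia are accompanied by a measured plasma glucose concentration" at or below that level, and for an asymptomatic one: "An event not accompanied by typical symptoms of hypoglycemia but with a measured plasma glucose concentration" at or below it.
- Section 7.5.6.3 starts treatment with 15 to 20 g of carbohydrate. If glucose is subsequently 50 mg/dL or less, "then the patient will be asked to consume 20 to 30 grams carbohydrate".
- Section 5.7 says: "If the measured SMBG is <70 mg/dL (3.9 mmol/L) or if the patient has symptoms suggestive of hypoglycemia", the patient can call the site. It adds: "The insulin dose will be altered by the Investigator or designee, if required, based on the values".

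The comments under the Appendix II tables mention carbohydrate content, activity and skipped meals as guides to the lispro dose. They do not mention low glucose or Section 5.7.

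**The concern.** Because the last mealtime row is open at the bottom, it covers hypoglycemic readings as well as normal ones. The same number can then be a hypoglycemic event under Section 7.5.6.1 and a target value under Appendix II. Under the asymptomatic definition the reading alone makes the event, so there need be no symptoms to alert the site.

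The table matches a routine visit task. Section 7.5.5 has the Investigator check at diary review, from the 8-point profiles, whether a dose change is needed. Under Section 7.2.4 and Appendix III those profiles hold three 2-hour post-meal readings on each of 3 days, which is the input the table asks for. Section 5.2 refers to a lispro titration scheme, and Appendix II contains the only one in the protocol. A site that used the table alone would see a hypoglycemic reading marked as satisfactory. Hypoglycemia is a secondary objective, and severe hypoglycemia is always an SAE in this trial.

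**Working it through.** The plan states no figure to reproduce. The check reads low values through both tables and sets the result against the cut-offs elsewhere in the protocol.

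**Inputs**

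- Basal rule (Appendix II): 71-130 mg/dL gives 0 U; 56-70 gives -2 U; below 56 gives -4 U.
- Mealtime rule (Appendix II): anything below 180 mg/dL gives 0 U and is labelled target.
- Hypoglycemia (Section 7.5.6.1 B and C): 70 mg/dL or less.
- Call trigger (Section 5.7): below 70 mg/dL, or symptoms.

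**Read-through**

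| Lowest value (mg/dL) | Basal table (fasting) | Mealtime table (post-meal) | Hypoglycemia under 7.5.6.1? | Section 5.7 trigger without symptoms? |
|---|---|---|---|---|
| 71 | 0 U | 0 U, target | No | No |
| 70 | -2 U | 0 U, target | Yes | No |
| 65 | -2 U | 0 U, target | Yes | Yes |
| 56 | -2 U | 0 U, target | Yes | Yes |
| 55 | -4 U | 0 U, target | Yes | Yes |
| 50 | -4 U | 0 U, target | Yes | Yes |

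Every row from 70 mg/dL down is hypoglycemia and is also on target in the mealtime table. At exactly 70 mg/dL without symptoms, Section 5.7 is not triggered either.

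**Example for one meal on 3 days.** Post-lunch readings of 110, 95 and 50 mg/dL have a lowest value of 50. The table returns target level and an unchanged dose.

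**A second sign that a floor is missing.** The comments under the tables tell the user to aim for the lower limit of the stated range. The mealtime range has no lower limit, so the instruction cannot be followed for lispro.

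**Effect of the proposed rows.** With 71-179 mg/dL giving 0 U and 70 mg/dL or less giving review, the old and new mealtime tables agree at every integer from 71 to 499 mg/dL. They differ only at 70 mg/dL or below.

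**The case against.** The best counter-argument is that the body of the protocol already handles low readings. Section 5.7 covers all insulin, Section 5.2 has the Investigator rather than the table tell patients their lispro doses, Section 7.5.5 has the Investigator review the profiles, and Sections 7.5.6.2 and 7.5.6.3 cover recognition and treatment. The appendix is only suggested guidance, and lispro titration is to be kept to a minimum. All of this stands and is why the point is minor. It does not remove the contrary label. Under Section 5.7 the patient may call and the dose is altered only if required, the section gives no post-prandial target, and Appendix II does not point to it.

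A second argument is that event classification and dose titration are different things. A hypoglycemic event caused by diet, alcohol or exercise need not lead to a lower prandial dose. That is also fair, and it is a reason to leave the size of any reduction to clinicians. It does not justify calling the reading a target.

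Third, the basal comparison is not like for like: fasting against post-meal glucose, and a basal dose against one also guided by the next meal and activity. Hence the basal unit steps should not be copied across. The comparison shows only that the same appendix puts a floor on one target and none on the other.

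Fourth, the 20 to 30 g step in Section 7.5.6.3 follows a first treatment and is acute care, not titration. That is correct; it shows only how the protocol regards such a value.

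**Conclusion.** The point holds, as a minor safety inconsistency. As printed, the mealtime table gives a wrong output for every lowest post-meal value of 70 mg/dL or less: target level, dose unchanged. It conflicts with the cut-off in Section 7.5.6.1 and gives no reference to Section 5.7. The protocol does not forbid a lispro reduction.

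The conclusion rests on the plain reading of the printed rows and on no numerical assumption. The documents do not say how often post-meal readings are 70 mg/dL or less, so no frequency of harm is claimed. Lispro is common to both arms, and no effect on the HbA1c comparison, the sample size or the analysis is claimed.

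**What to change.** In the Appendix II mealtime table, replace the last row with two:

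- 71-179 mg/dL (target level): maintain dose.
- 70 mg/dL or less: reduce dose / Investigator review per Section 5.7.

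The sponsor's clinicians should set the size of any unit reduction, since the documents give no basis for one. The new row itself prompts review at exactly 70 mg/dL, so Section 5.7 can stay as written. The new floor also gives the comment about aiming for the lower limit something to apply to.

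The cost is one row becoming two in one appendix table. Section 12 requires a written amendment, but the change can go in with other corrections. Visits, data collection, sample size and analysis are untouched.
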